### 5.3. Time Points

#### 5.3.1. Analysis Time Point Assignments

The designation of time points used for analysis (analysis time points) will be based on the actual day of assessment relative to the date of the first dose of IP in the study (relative day, ie, date of assessment – date of the first dose of IP in the study + 1), rather than the nominal visit recorded. Visits to be assigned with this method include the screening, Week 0 through Week 104, unscheduled, and early termination visits. The only exception is the assessments recorded at the post-treatment observational follow-up visit, which will be assigned to the follow-up visit.

All assessments performed prior to the date of the first dose of IP in the study will be assigned to the screening analysis time point. All assessments performed on the date of the first dose of IP in the study will be assigned to the Week 0 analysis time point.

The analysis time point assignments for the post-baseline visits (excluding the post-treatment observational follow-up visit) will be based on the relative day windows. These relative day windows are continuous, mutually exclusive, stretch from the date after the first dose of IP in the

study to the midpoint between the first 2 scheduled visits, from midpoint to midpoint between each successive pair of scheduled visits, and from the last midpoint onward for the last scheduled visit. If data are available on multiple days within a relative day window, then the assessment closest to the visit's target day (ie, study week  $\times$  7 + 1) will be used for that analysis time point. If the relative days from 2 assessments are equally close to, but on different sides of the target day, then the latter assessment will be used for that analysis time point. If multiple assessments are available on the same relative day, then the average of these assessments will be used for that relative day, except for the lab and ECG data for which the assessment at a later time of the same day will be used.

For efficacy analyses, the data after the date of treatment failure (Section 11.2) will be set to missing prior to the assignments of analysis time points.

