### 4.4. Sample Size Determination

A 2-group chi-square test with a 0.1 two-sided significance level will have approximately 80% power to detect a true 20% absolute difference (30% versus 10%) between a dose of apremilast and placebo, for the proportion of subjects achieving a clinical remission at Week 12 when the sample size in each group is 49. Assuming a dropout rate of 10% prior to Week 12, approximately 165 subjects (approximately 55 subjects per group) are planned to be randomized in this study.

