### 5.2. Safety Analysis Periods

For the safety analysis, the following analysis periods for post-baseline data are defined. Safety data in these periods are considered treatment-emergent.

- Weeks 0-12 placebo-controlled phase: This period encompasses data through Week 12. It starts on the date of the first dose of IP in the study, and ends on the date before IP dispensing at Week 12 for subjects who receive at least 1 dose of IP after Week 12 (defined as the date of the last dose of IP in the study no earlier than the date of IP dispensing at Week 12), or 28 days after the last dose of IP in the study or on the date of the actual last follow-up in the study, whichever comes first, for subjects who discontinue at or prior to Week 12.

Of note, this period is exclusive of the date of the first dose of IP in the study and inclusive of the date of IP dispensing at Week 12 for the analyses of the lab, vital signs, weight, and ECG data.

The safety analysis tables for the placebo-controlled phase will be presented by the following 4 groups: placebo, APR 30 BID, APR 40 BID, and APR total.

- Weeks 0-52 apremilast-exposure period: This period encompasses all apremilast-exposure data through Week 52, irrespective of when the apremilast exposure starts (at Week 0 or 12) in the study. It starts on the date of the first dose of apremilast in the study, and ends on the date before IP dispensing at Week 52 for subjects who receive at least 1 dose of apremilast after Week 52 (defined as the date of the last dose of apremilast in the study no earlier than the date of IP dispensing at Week 52), or 28 days after the last dose of apremilast in the study or on the date of the actual last follow-up in the study, whichever comes first, for subjects who discontinue at or prior to Week 52.

Of note, this period is exclusive of the date of the first dose of apremilast in the study and inclusive of the date of IP dispensing at Week 52 for the analyses of the lab, vital signs, weight, and ECG data.

The safety analysis tables, with an exception for the summaries of labs, vital signs, and body weight by time point, for the apremilast-exposure period during Weeks 0-52 will be presented by the following 4 groups: APR 30 BID, APR 40 BID, APR 30 BID/APR 40 BID, and APR total, as follows:

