### **11.2.3. Continuous Efficacy Endpoints**

#### **11.2.3.1. Primary Approach for Analysis**

For continuous efficacy endpoints, the primary missing data handling approach will be last observation carried forward (LOCF). For subjects who initially receive placebo and switch to an apremilast dose at Week 12 and subjects who initially receive APR 30 BID and switch to APR 40 BID at Week 12, the values on or before the date of IP dispensing at Week 12 will not be carried over beyond Week 12. For the TMS, PMS, and MMS, which are composite scores derived from individual subscores, the LOCF method will be applied to the individual subscores rather than to the composite score.

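### SAP 5.3.1 does not stop the Week 12 efficacy window at the Week 12 treatment switch, so the rule as written can select post-switch values for the placebo-controlled primary endpoint

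*SAP*

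**What the plan says.** SAP 5.3.1 sets analysis time points by relative day instead of nominal visit. Scheduled, unscheduled and early termination visits all feed the windows, which run "from midpoint to midpoint between each successive pair of scheduled visits". The assessment nearest the target day (7 × week + 1) is used. If two are "equally close to, but on different sides of the target day, then the latter assessment will be used for that analysis time point".

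The only efficacy data removed before windowing are those after a treatment failure. SAP 11.2.1 defines failure as a prohibited start or increase of UC medication, or a colectomy or ostomy. Starting study apremilast at Week 12 is neither.

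The SAP recognises the Week 12 switch in two other places:

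- SAP 5.2 makes the placebo-controlled safety period "inclusive of the date of IP dispensing at Week 12 for the analyses of the lab, vital signs, weight, and ECG data", so nothing after dispensing enters that period for subjects who continue on treatment.
- SAP 11.2.3.1 says that, for subjects who switch, "the values on or before the date of IP dispensing at Week 12 will not be carried over beyond Week 12". This covers continuous endpoints only. It stops pre-switch values moving forward and does not stop post-switch values entering Week 12.

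Protocol 4.2 places the primary measure, clinical remission by Total Mayo Score, within the Double-blind Placebo-controlled Phase at Week 12.

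**The concern.** The primary test is a placebo-controlled comparison at Week 12, but the Week 12 visit is also where the placebo control ends. Protocol 6.12.2 asks sites to try to witness the first dose from each new blister card, so the new treatment normally begins that day. The efficacy window stays open well beyond it.

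A value selected from after the switch is not a placebo value, and only the placebo arm changes from no drug to drug. The direction of the effect is not fixed. Protocol 1.4.2 says most diarrhea, nausea and headache events fall in the first 2 weeks of treatment, so early post-switch data could worsen the stool subscore and lower placebo remission. Early drug benefit could raise it.

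The same windowed values feed the other Week 12 endpoints. None of the sensitivity analyses in SAP 11.3.2 redefines the window.

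**Working it through.** **The plan's own figure.** SAP 4.4 states: "A 2-group chi-square test with a 0.1 two-sided significance level will have approximately 80% power". The assumed remission rates are 30% on apremilast and 10% on placebo, and the stated size is 49 per group. With pooled variance and no continuity correction:

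n = [1.645·√(2·0.2·0.8) + 0.842·√(0.3·0.7 + 0.1·0.9)]² / 0.2² = (0.931 + 0.461)² / 0.04 ≈ 48.4, rounded up to 49. Power at 49 is 80.4%.

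For the total, the SAP says: "Assuming a dropout rate of 10% prior to Week 12, approximately 165 subjects (approximately 55 subjects per group) are planned". 49 / 0.9 = 54.4, rounded up to 55, and 3 × 55 = 165. Both figures reproduce, and this point does not change them.

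**The window.** Target days are Week 8 = 57, Week 12 = 85 and Week 16 = 113. The midpoints are (57 + 85)/2 = 71 and (85 + 113)/2 = 99. The SAP does not say which window owns a midpoint day, so the last eligible day is 98 or 99. Protocol Table 4 allows the Week 12 visit at ± 3 days, Day 82 to 88. The Week 16 visit (Day 110 to 116) lies outside the window.

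**What the selection rule does for each visit day.**

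| Visit and switch day | Post-switch days still in the window | Post-switch days that replace a complete visit value |
|---|---|---|
| 82 | 16–17 | 83–88 (88 by the tie rule) |
| 83 | 15–16 | 84–87 (87 by the tie rule) |
| 84 | 14–15 | 85–86 (86 by the tie rule) |
| 85 | 13–14 | none |
| 86 | 12–13 | none |
| 87 | 11–12 | none |
| 88 | 10–11 | none |

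**Routes into the primary endpoint.**

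1. Replacement: an early visit followed by an unscheduled or early termination assessment. For example, with a visit on Day 83 and an unscheduled visit on Day 87, the Day 87 Physician's Global Assessment is used.
2. Filling: SAP 11.2.2.1 judges whether data are sufficient after time points are assigned. If a subscore is missing at the visit, a post-switch value up to Day 98 or 99 can supply it, and nonresponder imputation is not reached. This route does not need an early visit.
3. Diary: Protocol 6.7.1 requires continuous entry, so stool frequency and rectal bleeding data exist after the switch. SAP 5.3.2 states which diary days count at screening and baseline. No Week 12 rule is visible.

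**Size.** The documents give no share of subjects affected, so the following are assumed scenarios using an unstratified chi-square test.

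*Upper scenario, placebo remitters lost.* If visits were spread evenly over the 7 permitted days, 3/7 = 43% would switch before Day 85. Suppose all of these were exposed and a fraction q of their remitters were lost. Placebo remission is then 0.10 × (1 − 0.43q) against a true 10% in the apremilast arm. Exact enumeration with 55 per arm at two-sided 0.1 gives:

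| q | Placebo remission | Rejection favouring apremilast | Two-sided rejection |
|---|---|---|---|
| 0 | 10.0% | 5.1% | 10.3% |
| 10% | 9.6% | 6.0% | 10.4% |
| 25% | 8.9% | 7.5% | 11.1% |
| 50% | 7.9% | 10.9% | 13.2% |

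If only 5% were exposed, q = 50% gives 5.6% favouring apremilast and 10.4% two-sided.

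*Opposite direction, placebo remitters gained.* If 2%, 5%, 10% or 20% of placebo subjects were affected and remitted at 30%, placebo remission becomes 10.4%, 11%, 12% or 14%. Power at 49 per group falls from 80.4% to 78.7%, 75.9%, 71.1% or 60.7%.

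**The case against.** The strongest reply is that the gap rarely reaches the endpoint.

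- The Physician's Global Assessment is made at visits, and no scheduled visit falls between Week 12 and Day 99. Replacement therefore needs an early visit and then an unscheduled or early termination assessment within at most 6 days. This stands.
- Protocol 6.7.2 bars repeating the rectosigmoidoscopy within 4 weeks, so a post-switch endoscopy matters mainly when the Week 12 one was missed. This stands.
- The SAP's windowing list names visits, not diary days. Where a diary rule is visible, it looks back over several days from before the screening endoscopy. A reader might infer that after a Day 82 to 84 visit the Day 85 diary entry alone becomes the Week 12 subscore, exposing 43% of placebo subjects. The documents do not support that. No such single-day rule is stated, the Week 12 derivation may be redacted, and 43% also assumes evenly spread visits.
- Protocol 4.2 makes the intent clear. This helps the fix, but a program follows the stated rule, and the stated rule can depart from that intent.

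A reader might also infer that the rule favours apremilast. The documents give the timing of early diarrhea, not a rate of lost remission, and drug benefit would act the other way.

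**Conclusion.** The gap in the written rule is real. SAP 5.3.1 can put a post-switch value into the Week 12 primary endpoint, either by replacing an early visit's value or by filling a missing subscore ahead of nonresponder imputation. The cuts in SAP 5.2 and 11.2.3.1 do not reach it. Whether diary-based subscores are exposed cannot be settled from the visible text.

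The number of subjects affected is unknown and probably small, and the direction of bias is undetermined. The 10.9% one-directional rate (13.2% two-sided) is an assumed upper scenario resting on 43% exposure and q = 50%, neither of which the documents give. It also uses an unstratified test, not the planned stratified CMH test. The correction is worth making because it is cheap and protects the primary comparison, not because material inflation has been shown.

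**What to change.** Add to SAP 5.3.1, applied before windowing and in all arms: for subjects who receive Week 12 IP, efficacy assessments after the date of Week 12 IP dispensing are not eligible for the Week 12 or any earlier analysis time point. State also that the diary days used for the Week 12 stool frequency and rectal bleeding subscores must precede the first dose of Week 12 IP. Assessments made on the dispensing date itself stay eligible, which matches the treatment of laboratory, vital sign, weight and ECG data in SAP 5.2.

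With this cut, the post-switch assessment days eligible for the Week 12 window fall from 10–17 to 0. The cost is a short addition to the SAP and one programming condition on a date already used for the safety periods. The sample size is unchanged. The downside is that a few late values become missing and are handled by nonresponder imputation.

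Protocol 1.4.3 shows that Week 12 results have already been seen. If that analysis used the rule as written, count the subjects whose Week 12 values postdate dispensing, by arm, and report a rerun with the cut, labelled as post hoc.

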### **5.3.2. Screening and Baseline Definitions**

The screening SFS and RBS (involving the subject diary data) will be derived from the 3 earliest days with a non-missing value within a 7-day window that is allowed to be rolling within the 14 days of the screening visit, whereas the screening PGA is defined as the first assessment on or before the date of the first dose of IP in the study.

Unless otherwise specified, the baseline value is defined as the last assessment on or before the date of the first dose of IP in the study. The baseline SFS and RBS will be derived from the 3 most recent days (or as few as 2 days) with a non-missing value within the 7 days prior to the day before the screening endoscopy. In case of insufficient diary data during this period, the baseline value will be set to the screening value. The baseline TMS is calculated using the baseline SFS, RBS, PGA, and endoscopy subscores that are identified separately. The baseline PMS and MMS are calculated similarly.

For the safety analysis, the baseline value is defined as the last assessment on or before the date of the first dose of IP in the study for the analysis of the placebo-controlled phase, and the last assessment on or before the date of the first dose of apremilast for the analysis of an apremilast-exposure period.

## **5.4. Analysis Populations**

### **5.4.1. Intent-to-treat Population**

The intent-to-treat (ITT) population will be the primary population for the efficacy analysis. The ITT population will consist of all subjects who are randomized as specified in the protocol and receive at least 1 dose of IP. To assess change from baseline, a baseline value and at least 1 post-baseline value are also required. Subjects will be included in the treatment group to which they were randomized, irrespective of the treatments actually received.

### **5.4.2. Per-protocol Population**

A supportive analysis using the per-protocol (PP) population will be performed for the primary efficacy endpoint (clinical remission defined in the TMS) and the first secondary efficacy endpoint (clinical response defined in the TMS). The PP population will consist of all subjects included in the ITT population who have no protocol violations that may substantially affect the efficacy results. These protocol violations could include, but are not limited to, not meeting key

inclusion/exclusion criteria, gross IP non-compliance, receiving incorrect IP, treatment unblinding by the investigator, concomitant use of protocol-prohibited medications that are potentially effective for UC for an unrelated comorbid condition, not having the required assessment at the designated time point for reasons other than experiencing a treatment failure, or discontinuing due to lack of efficacy or a drug-related AE prior to the time point. The final determination on protocol violations, and thereby the composition of the PP population, will be made prior to the unblinding of the database for the Double-blind Placebo-controlled Phase analysis and will be separately documented. Subjects will be included in the treatment group to which they were randomized, irrespective of the treatments actually received.

#### **5.4.3. Safety Population**

The safety analysis for the placebo-controlled phase will be based on the safety population, which will consist of all subjects who are randomized and receive at least 1 dose of IP. At least 1 post-baseline assessment is required for inclusion in the analysis of each specific laboratory, vital sign, weight, or ECG parameter. To assess change from baseline, a baseline measurement is also required. Subjects will be included in the treatment group corresponding to the IP they actually received.

#### **5.4.4. Apremilast Subjects as Randomized Population**

The efficacy analysis during Weeks 12-104 will be based on the apremilast subjects as randomized population, which will include all subjects who are randomized (at Week 0) or re-randomized (at Week 12) to an apremilast dose group and receive at least 1 dose of apremilast. To assess change from baseline, a baseline value and at least 1 post-baseline value are also required. Subjects will be included in the apremilast dose group to which they were randomized or re-randomized.

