| SF-12v2 (Short Form 12-item Health Survey, version 2) | - | X | - | - | - | X | - | - | - | - | X | - | - | X | - | - |
| CCI | | | | | | | | | | | | | | | | |
| Dispense IP | - | X | X | X | X | X | X | X | X | X | X | X | X | X | - | - |
| Return and Count IP | - | - | X | X | X | X | X | X | X | X | X | X | X | X | X | - |

ECG=Electrocardiogram; ET= Early Termination Visit; CCI [redacted]; IP = Investigational Product; Obs. Follow-up=Post-treatment Observational Follow-up Phase; CCI [redacted]; PGA= Physicians Global Assessment; PMS= Partial Mayo Score; TMS= Total Mayo Score; UC= ulcerative colitis.

- ^a Subjects will be evaluated based on the TMS at the Week 12 Visit and will receive blinded active IP for an additional 40 weeks (Section 4.1).
- ^b At the Week 52 Visit, subjects who have a Mayo endoscopy score ≤1 will have the opportunity to participate in an Extension Phase and will receive apremilast 30 mg BID. With the implementation of Amendment 4, subjects currently in the Extension Phase who are receiving apremilast 40 mg BID will be switched to 30 mg BID at the next scheduled visit.
- ^c Subjects who discontinue from the study prior to the Week 52 Visit, or prior to the Week 104 Visit for subjects participating in the Extension Phase, will have the Early Termination Visit. Subjects who complete the Week 52 Visit and do not participate in the Extension Phase will not have the Early Termination Visit.
- ^d The Post-treatment Follow-up Visit will be conducted approximately 4 weeks after the last dose of IP for all subjects.
- ^e The female subject's chosen form of contraception must be effective by the time the female subject is randomized into the study (for example, hormonal contraception should be initiated at least 28 days before randomization). Contraception education is for males and Females of Child Bearing Potential (FCBP). Pregnancy testing will be performed 7 times during the study for FCBP. Serum pregnancy tests will be performed at Screening and urine pregnancy testing will be done at the Baseline Visit, Week 12, Week 52 (or at the Early Termination Visit if prior to the Week 52 Visit) and all visits during the Extension Phase. In addition, urine pregnancy testing will be done at the Early Termination

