6.7.2. Endoscopy

The screening endoscopy may consist of either a flexible rectosigmoidoscopy or a colonoscopy. A colonoscopy is required during the Screening Phase only for those subjects who have not had a colonoscopy within 12 months prior to the Screening Visit. Subsequent endoscopies (rectosigmoidoscopies) will be performed on Week 12 and Week 52, or at the Early Termination Visit if the Early Termination Visit occurs prior to Week 52. The flexible rectosigmoidoscopy will not be repeated within 4 weeks of the previous rectosigmoidoscopy. Rectosigmoidoscopy is not required during the Extension Phase or at the Early Termination Visit for subjects who discontinue the study during the Extension Phase.

Images of all endoscopic procedures (flexible rectosigmoidoscopy/colonoscopy) will be captured and sent to a centralized reader for their assessment, which will be used for the calculation of the TMS.

The screening endoscopy that is assessed by the central reader will be used to calculate the TMS to determine study eligibility. The Week 12 endoscopy assessment performed by the investigator will be used to calculate the TMS for the determination of subjects who do not achieve at least a 20% decrease from baseline in the TMS, at the Week 12 Visit. The Week 52 endoscopy assessment performed by the investigator will be used to determine eligibility for entry into the Extension Phase (Mayo endoscopy score ≤ 1).

CCI

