6.14. Study Completion

The End of Trial is defined as either the date of the last visit of the last subject to complete the study, or the date of receipt of the last data point from the last subject that is required for primary, secondary, and/or exploratory analysis, as pre-specified in the protocol and/or the Statistical Analysis Plan, whichever is the later date.

For the purpose of analysis, study completion for an individual subject is defined as reaching the Week 52 Visit. For subjects participating in the Extension Phase, completion of the Extension Phase for an individual subject is defined as completing the Week 104 Visit. Subjects not meeting this definition will be considered early termination subjects. All subjects are required to return for the Post-treatment Observational Follow-up Visit approximately 4 weeks after the last dose of IP.

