## 6. SUBJECT DISPOSITION

The number of subjects screened, the numbers and percentages of subjects randomized and not randomized, and of the eligibility criteria failed will be summarized based on all subjects screened.

The number and percentage of subjects included in the analysis populations will be summarized based on all subjects randomized.

Subject disposition (entered, completed, discontinued, along with primary reason for discontinuation) will be summarized based on all subjects randomized, unless otherwise specified below, for

- Weeks 0-12
- Weeks 0-52
- Weeks 12-52 (based on subjects who complete Week 12)
- Weeks 52-104 (based on subjects who enter the Extension Phase)
- Post-treatment observational follow-up phase (entered and completed only) within each of the above periods (based on subjects who enter the respective period)

The definitions of entry and completion in the above disposition summaries are given in [Table 2](#).

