#### 11.2.2. Binary Efficacy Endpoints

##### 11.2.2.1. Primary Approach for Analysis

For binary efficacy endpoints, the primary approach to handling missing data will be nonresponder imputation (NRI), where subjects who have insufficient data for response determination for the time point under consideration will be considered nonresponders for that time point. Insufficient data, including missing data at baseline (if the binary endpoint assesses change from baseline) or a post-baseline time point, will be determined after the handling of time points as described in Sections 5.3.

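### After Week 52, the readable efficacy rules impute visits that subjects outside the Extension Phase never have: nonresponse for binary endpoints, carried-forward scores for continuous ones

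*SAP*

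**What the plan says.** **Population.** SAP 5.4.4 states: "The efficacy analysis during Weeks 12-104 will be based on the apremilast subjects as randomized population". It defines that set as one "which will include all subjects who are randomized (at Week 0) or re-randomized (at Week 12) to an apremilast dose group", with at least one apremilast dose. It sets no condition about entering the Extension Phase.

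**Who has visits after Week 52.** Entry is optional and open only to subjects with a Mayo endoscopy score of 1 or less. Protocol 6.7.2: "The Week 52 endoscopy assessment performed by the investigator will be used to determine eligibility for entry into the Extension Phase". For everyone else, Protocol 6.14 says that "study completion for an individual subject is defined as reaching the Week 52 Visit", and footnote c of Protocol Table 4 adds: "Subjects who complete the Week 52 Visit and do not participate in the Extension Phase will not have the Early Termination Visit". The partial Mayo score (PMS) at Weeks 68, 86 and 104 is planned only for Extension participants (Protocol Summary, efficacy overview; Table 4).

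**Missing data.** For binary endpoints, SAP 11.2.2.1 applies nonresponder imputation (NRI): "subjects who have insufficient data for response determination for the time point under consideration will be considered nonresponders for that time point". No study phase is exempt. For continuous endpoints, SAP 11.2.3.1 makes last observation carried forward (LOCF) the primary approach. Its one readable stop covers subjects who change treatment at Week 12: "the values on or before the date of IP dispensing at Week 12 will not be carried over beyond Week 12". SAP 11.2.2.3 and 11.2.3.2 add data-as-observed (DAO) summaries by time point.

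**Other Weeks 52-104 analyses.** Disposition is "Weeks 52-104 (based on subjects who enter the Extension Phase"). Deviations (SAP 7) use the same group. The Weeks 52-104 safety, exposure and compliance summaries use subjects dosed after Week 52 (SAP 5.2, 9.1, 9.2, 12).

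**The concern.** A Week 52 completer who does not enter the Extension is not lost to follow-up. The design schedules nothing further for that person except the observational follow-up visit. NRI and LOCF nevertheless treat the absent Week 68, 86 and 104 visits as missing data and fill them in.

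For binary endpoints, the Week 104 rate then mixes two things: who entered, and who was responding among those who entered. PMS contains no endoscopy (Protocol 6.7.5). A subject with PMS remission at Week 52 and an endoscopy score of 2 would therefore count as a PMS nonresponder at Week 104 because of a variable outside the endpoint. If entry differs between dose groups, the rates differ even when response among entrants is the same.

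For continuous endpoints, a score last measured around the end of treatment is reported as a Week 104 value for someone who has been off treatment for a year. SAP 11.2.3.1 already guards against carrying values across the Week 12 switch. On the readable text it has no matching guard at Week 52.

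**Working it through.** **Plan's own figures.** The documents state no figure for Weeks 52-104. The sample size does reproduce: 30% versus 10%, two-sided 0.1 and 49 per group give 80.4% power; 49/0.9 = 54.4, rounded up to 55; 3 x 55 = 165. It is used here only to size the population.

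**Population size (SAP 5.4.4).** Two apremilast arms give 110. Placebo subjects re-randomized at Week 12, after the plan's 10% dropout, add 55 x 0.9 = 49.5. The total is about 160 (159.5).

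**Endpoints affected.** Table 4 schedules no endoscopy and no total Mayo score after Week 52, and the modified Mayo score needs endoscopy. What remains is PMS, its subscores, and SF-12v2 at Week 104 if it is analysed as a continuous efficacy endpoint.

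**NRI.** Let e be the share of the population entering and r the response rate among entrants. Rate shown = e x r. Neither value is in the documents; both are assumptions.

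| Enter (e) | Entrants | Not entering | r = 60% | r = 80% | r = 90% |
|---|---|---|---|---|---|
| 30% | 48 | 112 | 18% | 24% | 27% |
| 40% | 64 | 96 | 24% | 32% | 36% |
| 60% | 96 | 64 | 36% | 48% | 54% |

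**How much of the gap is design.** The gap between r and e x r is r x (1 - e). At r = 80% this is 56, 48 and 32 points for 30%, 40% and 60% entry. Those not entering include people who left before Week 52, for whom NRI is ordinary. Applying the plan's 10% to the two apremilast arms (and assuming all were dosed) gives 11 subjects gone before Week 12, worth 0.80 x 11/159.5 = 5.5 points. The gap due to by-design absence is then at most 50.5, 42.5 and 26.5 points. It shrinks further with dropout between Weeks 12 and 52, for which the documents give no figure.

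**Entry differing by dose.** With r = 80% in both groups, 40% versus 50% entry gives 32% versus 40%, an 8-point difference. With 40% versus 60% entry the difference is 48% - 32% = 16 points.

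**LOCF span.** From Week 52: 68 - 52 = 16 weeks, 86 - 52 = 34, 104 - 52 = 52. Table 4 also has PMS at the follow-up visit about 4 weeks after the last dose. SAP 5.3.1 keeps that visit as its own time point, and the readable text does not say whether LOCF may draw on it. So the carried value may not always be the Week 52 one.

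**LOCF mean.** If entrants average PMS 1.0 and carried values average 4.0 (both assumed), the Week 104 mean is e x 1.0 + (1 - e) x 4.0:
- 30% entry: 0.3 + 2.8 = 3.1
- 40% entry: 0.4 + 2.4 = 2.8
- 60% entry: 0.6 + 1.6 = 2.2

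The carried share is 70%, 60% and 40% respectively.

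**The case against.** **DAO tables are planned.** Only Extension participants have PMS after Week 52, so the DAO summaries already leave out non-entrants. A reader might infer that the plan would show 24% to 48% and nothing near the entrants' own rate. The documents do not support that. What remains is that NRI and LOCF are the named primary approaches, and that DAO also drops entrants who later discontinue, so it does not give NRI among entrants.

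**Redaction.** Every readable efficacy endpoint is at Week 8 or Week 12. SAP 11.5 and 11.6 and the further endpoints are blacked out. A restriction to entrants, or purely descriptive handling after Week 52, could be written there. This stands: the absence of such a rule cannot be asserted, only that SAP 5.4.4 and 11.2 neither contain one nor point to one.

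**Efficacy is not alone in keeping everyone.** The Weeks 0-104 safety period uses all apremilast subjects as treated, and laboratory, vital-sign, weight and ECG summaries have no separate Weeks 52-104 version. It would be wrong to call efficacy the single unrestricted analysis. Those safety periods do, however, end no later than 28 days after the last dose, and the readable safety text imputes no later visits.

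**Full-population NRI answers a fair question.** It gives the share of all who started apremilast who are still followed and responding at Week 104. Entrants are selected on good Week 52 endoscopy. This also stands: the full-population rate is not an error if it is labelled for what it is. The argument gives no support to LOCF for people who have left treatment.

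**Conclusion.** The point holds on the readable text, as a matter of denominator, labelling and carry-forward. SAP 5.4.4, 11.2.2.1 and 11.2.3.1 together impute Weeks 68 to 104 for subjects who have no such visits by design. The LOCF part is the clearer weakness: there is no readable stop at Week 52. The NRI part is a trade-off that needs an entrant-only summary and a clear label.

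The size cannot be fixed from the documents. The 24% to 48% range assumes 80% response among entrants and 30% to 60% entry. Not all of the shortfall can be charged to the entry rule, because dropout before Week 52 contributes. Nor does a carried PMS make anyone a sustained remitter: it is a score in a continuous table, not a responder classification.

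The primary and secondary efficacy endpoints (Weeks 8 and 12), the alpha and the sample size are unaffected. The conclusion is conditional on the sponsor confirming that the redacted sections hold no restriction. This is a change that should be made, not one on which the trial's main conclusion depends.

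**What to change.** 1. **Confirm.** Ask the sponsor whether SAP 11.5, 11.6 or the redacted endpoint text already limits efficacy after Week 52 to Extension entrants. If so, a cross-reference from SAP 5.4.4 and 11.2.3.1 is enough for whatever that text covers.
2. **Stop LOCF.** In SAP 11.2.3.1, state that no value is carried past Week 52 for subjects who do not enter the Extension, and say whether a follow-up-visit PMS may ever be carried.
3. **Add an entrant set.** For time points after Week 52, make the main maintenance summary NRI among subjects who enter the Extension and take at least one apremilast dose after Week 52. Label it as maintenance among selected entrants.
4. **Label the full-population rate.** If it is kept, title it as a composite of Extension entry and response, and show the number entering by dose group beside it.

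**Cost.** A few sentences and table titles. Entry is already defined in SAP Table 2, and the set dosed after Week 52 is already used for safety. The drawback is that entrants are selected on the Week 52 endoscopy, so their rates do not describe everyone who started apremilast, and dose comparisons among them are not protected by randomization.
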